4.1.3.1 Dose-Limiting Toxicities

For the purpose of this study, a DLT will be defined as *any of the following events occurring during the DLT window and not attributable to underlying disease or intercurrent illness*:

- Hematological toxicities defined as:
 - Grade 4 neutropenia (i.e., absolute neutrophil count [ANC] < 0.5×10^9 cells/L for a minimal duration of one week).
 - Grade 3 and 4 febrile neutropenia.
 - Grade 4 thrombocytopenia lasting > 48 hours
 - Grade 3 thrombocytopenia associated with bleeding episodes.

- Grade ≥ 3 non-hematological toxicity with the following exceptions:
 - Alopecia (any grade)
 - Grade 3 nausea or vomiting that resolves to Grade ≤ 1 with or without supportive therapy within one week.
 - Grade 3 hypophosphatemia and transient Grade 3 hyperbilirubinemia resolved within one week.
 - Grade ≥ 3 fatigue that resolves to Grade ≤ 2 within one week.
 - Fever $> 40^{\circ}\text{C}$ (i.e., Grade 3) that occurs within 48 hours of RO7172508 infusion and improves to $\leq 40^{\circ}\text{C}$ (Grade ≤ 2) within 48 hours and fully resolves within one week.
 - Grade 3 arthralgia that can be adequately managed with supportive care or that improves/resolves to Grade ≤ 2 within one week.
 - Grade 3 diarrhea, colitis, enteritis that resolves to Grade ≤ 1 within one week with no fever or dehydration.
 - Laboratory values of Grade ≥ 3 that are judged not clinically significant by the Investigator.
 - Grade 3 tumor pain that starts within 24 hours of infusion and improves/resolves to Grade ≤ 2 within one week.
 - Grade 3 hypoxia that starts within 24 hours of infusion and improves/resolves to Grade ≤ 2 within one week.
 - In participants with lung lesions, Grade 3 transient dyspnea secondary to localized lung edema that starts within 24 hours of infusion and resolves to Grade 1 or baseline within one week, and transient bronchospasm that resolves within 24 hours.
 - In participants with liver lesions, Grade 3 transient increase of bilirubin, transaminases (aspartate aminotransferase [AST]/alanine aminotransferase [ALT]) and/or gamma-glutamyl transferase (GGT) that starts within 24 hours of infusion and recovers to Grade 1 or baseline within one week.

Failure to recover from any RO7172508-related toxicity that results in a dose-delay of more than 14 days (any regimen) is defined as a DLT.

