3.1. ASSESSMENT OF SEVERITY

The terms "severe" and "serious" are not synonymous. Severity refers to the intensity of an adverse event (rated as mild, moderate, or severe, or according to a pre-defined grading criteria [e.g., National Cancer Institute Common Terminology Criteria for Adverse Events [NCI CTCAE] criteria); the event itself may be of relatively minor medical significance (such as severe headache without any further findings).

Severity and seriousness need to be independently assessed for each adverse event recorded on the eCRF.

Serious adverse events are required to be reported by the Investigator to the Sponsor immediately (i.e., no more than 24 hours after learning of the event).

The adverse event severity grading scale for the NCI CTCAE (v5.0) will be used for assessing adverse event severity. [Table 1](#) will be used for assessing severity for adverse events that are not specifically listed in the NCI CTCAE.

Table 1 Adverse Event Severity Grading Scale

Grade	Severity
1	Mild; asymptomatic or mild symptoms; clinical or diagnostic observations only; or intervention not indicated
2	Moderate; minimal, local, or non-invasive intervention indicated; or limiting age-appropriate instrumental activities of daily living ^a
3	Severe or medically significant, but not immediately life-threatening; hospitalization or prolongation of hospitalization indicated; disabling; or limiting self-care activities of daily living ^{b,c}
4	Life-threatening consequences or urgent intervention indicated ^d
5	Death related to adverse event ^d

NCI CTCAE = National Cancer Institute Common Terminology Criteria for Adverse Events.

Note: Based on the NCI CTCAE (v5.0).

^a Instrumental activities of daily living refer to preparing meals, shopping for groceries or clothes, using the telephone, managing money, etc.

^b Examples of self-care activities of daily living include bathing, dressing and undressing, feeding one's self, using the toilet, and taking medications, as performed by participants who are not bedridden.

^c If an event is assessed as a "significant medical event," it must be reported as a serious adverse event (see Section 6 of this Appendix for reporting instructions), per the definition of serious adverse event in Section 2.

^d Grade 4 and 5 events must be reported as serious adverse events (see Section 6 for reporting instructions), per the definition of serious adverse event in Section 2.

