3. PERSISTENT OR RECURRENT ADVERSE EVENTS

A persistent adverse event is one that extends continuously, without resolution, between participant evaluation time-points. Such events should only be recorded once on the Adverse Event eCRF. The initial severity of the event should be recorded, and the severity should be updated to reflect the most extreme severity any time the event worsens. If the event becomes serious, the Adverse Event eCRF should be updated to reflect this.

A recurrent adverse event is one that resolves between participant evaluation time-points and subsequently recurs. Each recurrence of an adverse event should be recorded separately on the Adverse Event eCRF.

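### The hematological DLT items are inconsistent by grade: short Grade 4 thrombocytopenia with minor bleeding meets no item although Grade 3 with the same bleeding does, and Grade 5 febrile neutropenia is left unplaced

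*Combined protocol and SAP*

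**What the plan says.** Section 4.1.3.1 defines a DLT as "any of the following events occurring during the DLT window and not attributable to underlying disease or intercurrent illness". Four hematological items follow. Those at issue are "Grade 4 thrombocytopenia lasting > 48 hours", "Grade 3 thrombocytopenia associated with bleeding episodes" and "Grade 3 and 4 febrile neutropenia". The fourth is Grade 4 neutropenia lasting at least a week.

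Two further routes exist in the same section. One is Grade 3 or higher "non-hematological toxicity with the following exceptions". The other is a delay clause: "Failure to recover from any RO7172508-related toxicity that results in a dose-delay of more than 14 days (any regimen) is defined as a DLT".

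Three other places decide what happens to a case the list misses:

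- Section 9.3, Table 21: only participants who finished the window free of DLTs, or who had one, are DLT-evaluable and used for the MTD.
- Appendix 3, section 3: for a persistent event, "the severity should be updated to reflect the most extreme severity any time the event worsens". The severity scale in Appendix 2, section 3.1 includes Grade 5, "Death related to adverse event".
- Section 4.1.2.2: the logistic model is updated with the binary DLT outcome before a new cohort opens.

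**The concern.** A toxicity list that feeds a dose-escalation model should be monotone: if an event counts at one grade, a worse grade of the same event should count too. Here it need not. The section writes Grade 3 and 4, or Grade 3 or higher, where it means several grades, so the bare Grade 3 in the bleeding item reads as Grade 3 only.

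At stake is the 0/1 outcome that drives the mCRM-EWOC recommendation and the MTD, which is the primary objective. With cohorts of about 3, one miscoded participant usually moves the next dose. If it would have been the first DLT, it also keeps the 100% increment cap in force where the plan would otherwise allow 50%. The miscoded outcome then stays in every later MTD estimate.

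**Working it through.** **Step 1. Apply the items literally** (events inside the window, not due to disease or intercurrent illness; the 36 hours is illustrative):

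| Case | Item met | Place in the MTD model |
|---|---|---|
| Grade 3 thrombocytopenia, Grade 1-2 bleed | Bleeding item | DLT |
| Grade 4 thrombocytopenia for 36 hours, same bleed, window completed | None: too short for the Grade 4 item, wrong grade for the bleeding item, bleed below Grade 3 | No DLT |
| Grade 3 or 4 febrile neutropenia | Febrile neutropenia item | DLT |
| Febrile neutropenia recorded as Grade 5, death inside the window | None if the recorded grade decides | Window not completed and no listed DLT, so outside the DLT-evaluable population |

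For the last row, the replacement reasons in section 7.1 cover failure to complete the window for non-drug-related reasons only, so a drug-related death has no clear place there either.

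**Step 2. Reproduce the plan's figure.** Inputs, all from Appendix 8, section 1.2: logit p(d) = α + β ln(d/100), with (α, log β) from the printed two-component normal mixture, weights 10/90; the printed dose grid; cohorts of 3 with no earlier DLTs. The next dose maximises P(0.20 ≤ p ≤ 0.35), subject to P(p > 0.35) < 0.25 and an increment cap of 100% with no DLT or 50% from the first. With 200,000 prior draws, all nine 0-DLT rows of Table 1 are reproduced exactly. Eight of the nine 1-DLT rows are exact, and the ninth is 9.6 against the printed 9.5 mg. Section 1.2.1 also prints a weight of 0.25; these rows are the same with it.

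**Step 3. Code one true DLT as none.** Columns 2 and 3 are Table 1 as printed. Column 4 is their ratio. Column 5 is P(p > 0.35) at the column 3 dose, computed from the true data (1 DLT in 3) with the 10/90 prior.

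| Current dose, mg | Next dose, 1 DLT | Next dose, 0 DLT | Ratio | Overdose probability, % |
|---|---|---|---|---|
| 1.6 | 2.4 | 3.2 | 1.33 | 20.5 |
| 3.2 | 4.8 | 6.4 | 1.33 | 15.3 |
| 6.4 | 9.5 | 12 | 1.26 | 13.3 |
| 12 | 18 | 20 | 1.11 | 11.2 |
| 20 | 30 | 40 | 1.33 | 14.2 |
| 40 | 60 | 80 | 1.33 | 18.3 |
| 80 | 120 | 150 | 1.25 | 21.2 |
| 150 | 200 | 300 | 1.50 | 27.7 |
| 300 | 400 | 400 | 1.00 | 21.2 |

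The next dose rises at eight of nine levels. The 25% limit is passed at one, 150 to 300 mg. With the 0.25 weight that value is 23.0%, and no level passes the limit.

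**Step 4. Drop the participant instead** (the death inside the window). The model's next dose for 0 DLTs in 2 equals that for 0 in 3 at every level, so the signal is lost here too. Section 4.1.2.2 would still require a third evaluable participant before the next cohort opens.

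**The case against.** The strongest reply is that little slips through. A Grade 3 or higher bleed, or a fatal sepsis reported as its own event, is a non-hematological DLT. Bleeding that continues while platelets pass through Grade 3 may meet the bleeding item. A related delay of more than 14 days is a DLT by itself. Escalation also rests on all safety data and on consensus, and judgment may override the model (synopsis; sections 4.1.5 and 4.2.1). All of this stands, and it makes the gap narrow. It does not close it: a short Grade 4 episode with a Grade 1-2 bleed can miss every route, and a review that holds back a dose leaves the model's 0/1 input as it was.

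A reader might infer that a fatal febrile neutropenia is entered as no DLT. The documents do not support that for a death inside the window: by Table 21 such a participant would be non-evaluable. Entry without a DLT could arise only if onset is inside the window and death follows its completion. A fatal case will also usually have passed through Grade 3 or 4, which the item names. Appendix 3 governs the grade recorded on the eCRF and does not say that a DLT already met is cancelled. The text leaves open whether the earlier grade or the recorded Grade 5 decides.

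A reader might also infer that a miscoded event generally pushes the trial past its overdose limit. For a single missed DLT it does so at one level of nine, and only under the 10/90 weight.

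**Conclusion.** The thrombocytopenia inconsistency is real and follows from the printed list: the worse event can count as no DLT where the milder one counts as a DLT. The febrile neutropenia item is an ambiguity, whose literal consequence for a death in the window is loss of the participant from the MTD analysis.

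One miscoded event raises the next recommended dose at eight of nine levels, by a factor of 1.11 to 1.50, with an overdose probability of 11-28% at the dose then chosen. These figures assume cohorts of 3, no earlier DLTs, the Appendix 8 IV model, and a dose taken as the model recommends it. The documents give no frequency for these events. They should be rare, so this is a correction worth making to the definition of the primary safety variable, not a sign that the escalation design is unsound.

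**What to change.** The sponsor should reconcile the hematological items of section 4.1.3.1 with each other, with the DLT-evaluable definition in section 9.3 (Table 21), and with the worst-grade recording rule in Appendix 3, section 3. Two properties are needed:

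- A higher grade of the same hematological event never counts less than a lower grade.
- The text states how a Grade 5 event in the DLT window enters the MTD model, and whether an earlier grade or the recorded worst grade decides DLT status.

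Which events should limit dose is for the sponsor and the investigators to decide; no threshold is proposed here. The cost is a few words in the DLT definition and the population table. The small downside is that a rare additional event may count as a DLT.

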During the course of this study, the need for obinutuzumab pretreatment will be assessed based on loss of RO7172508 exposure and/or ADA-related safety events. Details, including decision criteria, are provided in Section 4.1.3 and Appendix 9. If on-target toxicity is reported predominantly in the first cycle of treatment, fractionated dosing may be implemented for the first cycle to improve tolerability. RO7172508 treatment would start with 10% of the planned dose on Cycle 1 Day 1, 30% of the planned dose on Cycle 1 Day 8 and 60% of the planned target dose on Cycle 1 Day 15, followed by the full dose treatment from Cycle 2 Day 1 onwards as described in Figure 2. By using a step-up fractionated dosing approach, it is predicted that the lower peak exposures (C_{max}) will result in lower cytokine levels to that when the full dose is given on Day 1. The fractionated dosing regimen may be adjusted depending on emerging data and in discussion with the Investigators. A similar approach to increase the dose administered during the first three weeks as applied with dose-fractionation in the Q3W treatment group, may also be employed in the once weekly (QW) treatment group. If a patient in the fractionated dose cohort experiences any adverse event that results in a delay of the next administration of RO7172508 beyond one week, the dose at which the treatment should be restarted will require agreement between the investigator and the Sponsor.

Figure 2 Fractionated Dosing Design for Q3W and QW

At least 3 evaluable participants will be treated in each cohort during the IV or SC dose-escalation regimen.

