The Part II dose-escalation will start with a dose of 1.6 mg (flat dose) IV Q3W (Section 4.3 Dose Justification) if this dose has been reached in Part I and considered safe. In the eventuality that Part I has been stopped because of the occurrence of a RO7172508-related Grade ≥ 2 AE (or DLT) then, the starting-dose of Part II will not exceed the dose-level at which the AE that delineated the end of Part I occurred. Furthermore, the grade and type of AE will also be considered, when choosing the dose-level for Part II. In the eventuality that the Sponsor decides to initiate Part II in the absence of an observed RO7172508-related Grade ≥ 2 toxicity and prior to the dose-level reaching 1.6 mg, then the starting-dose of Part II will not exceed the highest dose tested in Part I. If the starting-dose of Part II is the same as the last dose in Part I, the participant treated at the last dose in Part I could be considered as the first participant of the cohort for Part II. If the initial dose is not tolerated, then participants for the subsequent cohort may be enrolled at a lower RO7172508 dose than the initially selected Part II starting-dose. The maximum dose of RO7172508 will be 400 mg (flat dose IV). The initial dosing regimen in Part II may also be adapted depending on emerging data in Part I.

In Part II dose-escalation, a minimum of 3 participants per cohort *will be enrolled who have a baseline sCEA level ≤ 20 ng/ml*. Participants within a cohort will be treated in a sequential manner with one week between the first and second participant, and at least one day between subsequent participants. However, if the first participant experiences a DLT within the first 7 days, then the time between the treatment of subsequent participants within the same cohort may be increased. The DLT evaluation window in Part II is defined as a period of 3 weeks after the first administration of RO7172508 in an IV Q3W schedule. Based on emerging data, the interval between dosing of each participant within a cohort or the DLT window may be adjusted if deemed appropriate by the Investigators and/or the Sponsor.

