For each cohort, all participants will be followed through a 3-week DLT window (i.e., 21 days *after the first dose of RO7172508*). If fractionated dosing is implemented in Cycle 1 to improve tolerability, the DLT window will be extended to include the cycle where the planned target dose is administered in full i.e., *Cycle 1 Day 1 until the end of Cycle 2*. The DLT window will therefore be 6 weeks (42 days), or 8 weeks (56 days) if treatment has been delayed for no more than 14 days.

A new cohort can be opened when at least 3 evaluable participants of the previous cohort have completed the DLT window. *At least 3 evaluable participants must have a baseline sCEA level of ≤ 20 ng/ml.* If participants experience a DLT before completion of the last day of their DLT window, they will be considered as having completed their DLT window. Prior to opening a new cohort, the logistic regression model will be updated with the treatment outcome (i.e., the occurrence of DLT) and a new estimate of the MTD will be derived.

Enrollment into the next cohort will only resume after the Sponsor and the Investigators have jointly decided on the next dose-escalation step. Subject to clinical judgment, a new cohort of participants will be dosed at the new estimate of the MTD or the highest allowable dose based on pre-specified safety constraints as described below, whichever is lower and as guided by the mCRM-EWOC model. The design will continue as described, assigning participants to the MTD as estimated from all of the DLT data cumulatively, until one of the pre-defined stopping criteria is satisfied (see Section 4.1.4) or the pre-determined sample size of 60 DLT-evaluable participants is reached, whichever comes first. *Depending on emerging PK and safety data, the dose escalation may be evaluated taking into account sCEA levels at baseline in a sensitivity analysis (i.e. dose escalating more conservatively in the event toxicity is associated with low baseline sCEA levels).*

Built-in safety constraints are in place to prevent exposing participants to undue risk of toxicity, i.e., for Q3W dosing schedule, maximum allowable dose-increment, in absence of DLT, will be a maximum of 100%; if one DLT occurs then, an increment of 50% maximum will be allowed. The maximum dose that could be assessed in Part II will be 400 mg IV (see Section 4.3).

Provisional dose-levels in absence of DLT are listed in [Table 9](#).

Table 9 Provisional Dose Levels in Absence of DLT

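### In Part II, for the dose due just after the DLT window (and the weekly SC Day 15 dose), the more-than-14-day delay DLT is established only after the window, so a participant on hold is coded as a non-DLT at the escalation decision

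*Combined protocol and SAP*

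**What the plan says.** Section 4.1.3.1 defines a DLT as "any of the following events occurring during the DLT window and not attributable to underlying disease or intercurrent illness". After the list of hematological and non-hematological criteria it closes with one more: "Failure to recover from any RO7172508-related toxicity that results in a dose-delay of more than 14 days (any regimen) is defined as a DLT".

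Section 4.1.2.2 sets the window: "The DLT evaluation window in Part II is defined as a period of 3 weeks after the first administration of RO7172508" on the IV Q3W schedule. The SC cohorts use the same window. With fractionated dosing it becomes 42 days, or 56 days if treatment was delayed by no more than 14 days. Section 4.1 describes fractions on Days 1, 8 and 15, "followed by the full dose treatment from Cycle 2 Day 1 onwards".

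On escalation, section 4.1.2.2 says "A new cohort can be opened when at least 3 evaluable participants of the previous cohort have completed the DLT window". Table 21 makes a participant evaluable either by completing the window without a DLT or by having reported one. The increment cap is 100% until the first DLT and 50% from then on (section 4.1.2.2; Appendix 8, section 1.2.4). Section 6.6 permits holds of up to two cycles for toxicity to resolve.

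**The concern.** The delay criterion catches related toxicity that the other criteria miss but that still stops redosing:

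- Grade 3 hypoxia, tumor pain, fatigue and arthralgia are exempt in 4.1.3.1 if they improve to Grade 2 within a week, yet 6.6 requires Grade 1 or less before redosing.
- Grade 2 diarrhea (Table 19) and Grade 2 tumor inflammation (Table 18) are held.
- Grade 3 neutropenia without fever and Grade 3 thrombocytopenia without bleeding are not DLTs, yet 6.6 requires Grade 2 or less.

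If the window closes as the next dose falls due, such a participant has completed the window without a DLT on the day the cohort is assessed. No text makes that participant pending. In a first-in-human trial of a T-cell engager, the next cohort could then open under the larger increment cap while a toxicity that will meet the sponsor's own DLT definition is unresolved.

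**Working it through.** **1. The plan's own figures.** One 21-day cycle = 21 days; two cycles = 42; 42 + 14 = 56. The stated windows reproduce.

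**2. When the criterion is first met.** With Day 1 = first dose, a delay exceeds 14 days on due day + 15.

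| Regimen and held dose | Due | First met | Window | Inside? |
|---|---|---|---|---|
| Q3W (IV or SC), C2D1 | 22 | 37 | 21 | no |
| SC QW, Day 8 | 8 | 23 | 21 | no, by 2 days |
| SC QW, Day 15 | 15 | 30 | 21 | no |
| SC QW, C2D1 | 22 | 37 | 21 | no |
| Fractionated, Day 8 / Day 15 / C2D1 | 8 / 15 / 22 | 23 / 30 / 37 | 42 | yes |
| Fractionated, C3D1 | 43 | 58 | 42 | no |
| Fractionated with C2D1 14 days late, C3D1 | 57 | 72 | 56 | no |

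In the fractionated schedule the criterion works for every dose up to C2D1. It fails for toxicity from the first full dose, which delays C3D1. Counting the first dose as Day 0 shifts days by one and changes nothing.

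**3. Against the escalation date.** Section 4.1.2.2 sets the stagger: "Participants within a cohort will be treated in a sequential manner with one week between the first and second participant", then at least one day. The earliest first doses are Days 1, 8 and 9.

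- Q3W or QW: earliest decision 9 + 21 = Day 30. A C2D1 hold is established on Days 37, 44 and 45 for participants 1 to 3, which is 7, 14 and 15 days late.
- SC QW, Day 15 hold: Days 30, 37 and 38, which is 0, 7 and 8 days late.
- SC QW, Day 8 hold: Days 23, 30 and 31, at most 1 day late, so this case hardly matters.
- Fractionated: earliest decision 9 + 42 = Day 51. A C3D1 hold is established on Days 58, 65 and 66, again 7, 14 and 15 days late.

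If the next Q3W cohort starts at once (Days 30, 37, 38), the number dosed strictly before the delay of participant 1, 2 or 3 is established is 1, 3 and 3. The documents give no decision lag. With an assumed lag of 7 days the counts are 0, 1 and 2; with 15 days they are 0, 0 and 0. The counts for a fractionated C3D1 hold are the same, but the next cohort's first full dose is on Day 51 + 21 = 72, so by Day 66 it has received only fractions.

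**4. Effect on the next dose.** Appendix 8 Table 1 (cohorts of 3, no earlier DLT) gives the next dose after 0 versus 1 DLT:

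| Current dose, mg | 0 DLT | 1 DLT | Ratio |
|---|---|---|---|
| 1.6 | 3.2 | 2.4 | 1.33 |
| 3.2 | 6.4 | 4.8 | 1.33 |
| 6.4 | 12 | 9.5 | 1.26 |
| 12 | 20 | 18 | 1.11 |
| 20 | 40 | 30 | 1.33 |
| 40 | 80 | 60 | 1.33 |
| 80 | 150 | 120 | 1.25 |
| 150 | 300 | 200 | 1.50 |
| 300 | 400 | 400 | 1.00 |

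Recomputing these rows by Monte Carlo from the stated priors, reference dose, grid and caps reproduces every 0-DLT and 1-DLT entry from 1.6 to 150 mg, except 9.6 instead of 9.5 mg after 6.4 mg (one grid step).

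With one DLT scored but the 100% cap kept, the model returns the 0-DLT dose at every step from 1.6 to 80 mg. At those 7 steps the whole difference is the 50% cap. The 1.50 after 150 mg is partly a grid effect: the cap allows 225 mg, the grid moves in 50 mg steps, and 300/225 = 1.33.

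**The case against.** The strongest reply has four parts.

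**The DLT is not lost.** A reader might infer that it drops out and biases the MTD. The documents do not support that. Table 21 includes anyone who reported a DLT, and section 4.1.2.2 has the model continuously updated and the MTD estimated from cumulative data. The better reading is late counting. This stands, and leaves a timing defect only.

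**Escalation is not automatic.** Section 4.1.2.2 requires a joint decision, 4.1.5 a consensus that may include expanding a cohort, and 4.2.1 lets clinical judgment override the model. Section 4.3.1 requires a full safety evaluation and allows smaller increments. Also, "the interval between dosing of each participant within a cohort or the DLT window may be adjusted if deemed appropriate". These make the held participant visible and reduce the risk. They are discretionary, and none changes how that participant is coded or when the 50% cap takes effect.

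**The higher dose is usually still within the overdose limit.** A reader might infer that the 0-DLT dose is unsafe by the plan's own standard. With one DLT in three scored, the recomputed overdose probability at that dose is 0.11 to 0.21 at 8 of 9 steps, below the 0.25 limit. Only 300 mg after 150 mg exceeds it (0.28). This stands: what is lost is mainly the 50% cap, although that is itself a stated safety constraint.

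**The 3-week window is reasoned.** Section 4.2.1 notes that toxicity with the in-class agent came mostly in the first few days, and most other Grade 3 or higher non-hematological toxicity is already an in-window DLT. This narrows the affected class but does not remove it.

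**Conclusion.** The concern holds as a timing defect in Part II. For the first dose due after the window, and for the weekly SC Day 15 dose, the delay criterion cannot be established before the window ends. Followed literally, the rules code a participant on hold for related toxicity as a non-DLT at the model update, and the next cohort may open under the 100% cap.

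Its size is limited. The cap effect applies only to the trial's first DLT; after that the cap is already 50% and only the model input changes. Early dosing of 1 to 3 next-cohort participants after a Q3W hold needs minimum stagger and no lag between the last window end and the next dosing. Slower accrual shrinks it too, and each cohort needs 3 evaluable participants with sCEA of 20 ng/mL or less. The documents give no frequency for such holds, so none is assumed.

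It would be wrong to say that the criterion fails in every regimen, since fractionated delays up to C2D1 are captured. Part I is not included either: under section 4.1.2.1 a related Grade 2 or higher event there already blocks the next cohort or triggers the switch to Part II. The change is worth making because following the stated rules gives the wrong coding when it matters, and the correction is cheap.

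**What to change.** 1. In 4.1.3.1, state that RO7172508-related toxicity arising in the DLT window that delays the next dose by more than 14 days is a DLT even if the delay is completed after the window, for all regimens (including C3D1 after fractionated dosing).
2. In 4.1.2.2 and Table 21, treat a participant whose next dose is on hold for related toxicity at window end as pending, not as a completer without a DLT. Pending ends in one of three ways: redosed within the limit (non-DLT); delay beyond 14 days, or treatment permanently stopped for that toxicity (DLT); or departure for an unrelated reason (not evaluable, replaceable under 7.1).
3. Escalation waits only if fewer than 3 other qualifying evaluable participants, including the sCEA requirement, have completed the window. Otherwise the pending participant is left out of the update and added when resolved.

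The cost is a few sentences and a wait of at most about 15 days (0 to 8 days for a held SC QW Day 15 dose), only in affected cohorts. In a minimum cohort of 3 there are never 3 others, so one participant on hold always triggers the wait.
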